6.1.2 Secondary study endpoints

- The outcome of patients with an indication for cyst resection (treated and non-treated), in terms of the number of operated patients, surgical procedures, morbidity, mortality, and cyst recurrence (Table II and III).
- Cyst evolution, in terms of development of symptoms, cyst growth, nodules, and secondary pancreatic duct dilatation.
- The perceived burden of surveillance for participants, as assessed by questionnaires regarding attitude towards surveillance and general anxiety and depression (Hospital Anxiety and Depression scale, HADS) (Table V) [15-19].

6.1.3 Other study endpoints

- To identify possible risk factors for malignancy, either patient or cyst related (Table IV).
- To identify useful biomarkers for malignancy
- To design more efficient and cost-effective surveillance strategies, by building a micro-simulation screening analysis (MISCAN) model, based on the outcome data of this study.

6.2 Randomisation, blinding and treatment allocation

Not applicable

6.3 Study procedures

After informed consent is obtained, the treating physician will receive online information regarding the surveillance strategy, as formulated in the consensus statement (Figure 2). Baseline characteristics will be filled out on the on-line CRF (patient and cyst characteristics, previous pancreatic surgery). The surveillance will take place at the hospital of origin. The treating physician will coordinate the surveillance. They will be reminded about follow-up dates by email.

Follow-up schedule and imaging studies

Follow-up is recommended at one-year intervals, except for newly diagnosed cysts with a diameter of ≥ 1 cm, for whom 6 months intervals are advised during the first year. According to the consensus statement, the follow-up frequency should increase after 5 years, to every 6 months. However, as this particular recommendation lacks all scientific justification, the decision to increase the follow-up frequency of the study population will not be made until 2017, after a preliminary analysis is performed.

Based on the consensus statement, cyst surveillance will be performed by MRCP. EUS will serve as an alternative, according to the preference of the treating physician. Switches in follow-up modality are permitted. The local radiologist is provided with instructions regarding the aspects that need to be addressed in the imaging report. If patients have more than one cyst, the specifications of the three largest cysts will be recorded and worrisome features will be monitored for all cysts.

To ascertain the reproducibility and quality of the MRI reports, 100 imaging studies will be selected at random and sent to the Erasmus Medical Center, for re-evaluation by a radiologist (TB). Discrepancies will be recorded and used to calculate the inter observer variability. For this reason, imaging studies should be stored at the hospital of origin. On request, during the study, this radiologist (TB) can be consulted for advice or a second opinion, in case of diagnostic difficulties.

Pathological analysis and tissue handling

The pathology department will handle the cyst fluid; at least 0.5 ml is centrifuged to generate deposit and supernatant fluid. The deposit will be used to process a smear and/or cellblock, for pathological analysis. The supernatant fluid will be sent out to the laboratory for biochemical analysis (CEA, CA 19.9, amylase). If at least 0.5 ml of the cyst fluid is left after the above mentioned procedures, this should be stored and frozen at

minus 80 degrees Celsius, for future molecular analysis. This step will be omitted in centers without such freezing facilities.

The pathologist will be provided with a protocol regarding the aspects that need to be addressed in the pathology report. On request, the pathologist of the investigators team (KB) can be consulted for advice or a second opinion. If surgery is performed, a glass slide of the pathological specimen (or a histological sample, preserved in formalin) must be sent to the pathology department of the Erasmus Medical Center in Rotterdam, for revision.

Laboratory investigations

To determine the serum CA 19.9 level, a blood sample of at least 6 ml must be collected. For each hospital, the local laboratory technique and cut-off value for CA 19.9 will be applied and recorded. In addition, for future genetic testing, two additional 6 ml blood samples will be drawn (one EDTA, one Serum tube) and stored at –20 and -80 degrees Celsius, respectively. This only applies for participating centers with such facilities.

Collection and storage of samples

All human samples that are collected during the study will be stored locally. If local facilities are not sufficient, samples may be sent to the Erasmus University Medical Center Rotterdam, for storage.

Patient questionnaires

Patients with a newly diagnosed cyst will be asked to fill out a questionnaire at home (Table V). This questionnaire will be sent to them by email (if they gave permission to do so) at study entry, after every follow up visit for the first three years, once after 5 and 10 years, and after cyst related events. The questionnaire can be filled out on-line, which will take approximately 5 to 15 minutes. Patients who fail to respond to the questionnaire will be reminded by email after two weeks. Patients who do not want to provide their email address will be able to join the study, without participating in the questionnaire evaluation.

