2. OBJECTIVES

Primary objective

To establish the yield of regular pancreatic cyst surveillance, based on a recently published European experts consensus statement, in terms of identified patients that require cyst resection, diagnosed malignancies, cyst evolution, and the perceived burden for participants.

[figure not shown]
Secondary objective

To identify more (cost) effective surveillance strategies, using acquired information on the natural course of the disease, identified risk factors for malignancy, and calculations from a MISCAN model for cyst surveillance.

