4.4 Sample size calculation

In total, we aim to include 5000 patients during the study period of 10 years, of which 250 patients per year will be included in the Netherlands. This will provide over a 1000 patient years after three years, even in the case of expected loss to follow-up (15% of

patients included in the first year, 10% of those included in the second year, and 5% included in the third year). Internationally, depending on the number of cooperating centres throughout Europe, we expect to include between 250 and 500 patients yearly.

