6.6 Follow-up of subjects withdrawn from treatment

These subjects will receive routine care from their treating physician.

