10.1.3 Privacy rules

The handling of personal data will comply with the Dutch Personal Data Protection Act (in Dutch: De Wet Bescherming Persoonsgegevens, Wbp). All outcome data will be provided by the treating physician through a secured, online eCRF. Patients will be identified in the eCRF by study-number. The investigators will keep an identification log, consisting of the information to link source records to the eCRF.

Patients will complete their questionnaires online. For this purpose, patients will be asked to provide their email address in the informed consent form. This email address will be stored in a separate database, and will only be used to send an email to the patient after every visit. The link between email address and patient is not visible for unauthorized persons and will only be used to serve as an identification key for the electronic system, to be able to couple the study number in the main eCRF to the corresponding respondent in the questionnaire database.

The data are stored and processed using a database program for personal computers. Anonymous data are stored separately from identifiable data (i.e. a patients email address), so that it is impossible to couple research data to specific individuals. All data that leaves the investigational site will be blinded and

anonymized. Only authorized study team members are able to view certain non-anonymous data. For analysis, the anonymous study data from both the clinical and the questionnaire database will be exported and subsequently coupled. From this overall mother-database, data will be transferred to a statistical program. Only anonymized data will be transferred to the statistician for further analysis.

The subjects will be informed that the data will be stored on paper and electronically, that local regulations for the handling of computerized data will be followed as described in the written patient information, and that identification of individual patient data will only be possible for the coordinating and principal investigator. Furthermore, the subjects will be informed about the possibility of inspections of relevant parts of the hospital records by health authorities. These officials will be identified and have signed a confidentiality agreement.

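### Between study entry and year 5 the burden questionnaire is triggered only by a follow-up visit (years 1 to 3) or a cyst-related event, so patients who silently skip or stop surveillance go unmeasured

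*Protocol*

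**What the plan says.** Section 2 counts "diagnosed malignancies, cyst evolution, and the perceived burden for participants" among the components of surveillance yield in the primary objective. Section 6.1.2 lists as a secondary endpoint "The perceived burden of surveillance for participants, as assessed by questionnaires regarding attitude towards surveillance and general anxiety and depression".

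Under section 6.3 the questionnaire goes to patients with a newly diagnosed cyst who give an email address. It is sent at study entry, then "after every follow up visit for the first three years, once after 5 and 10 years, and after cyst related events". For non-response, "Patients who fail to respond to the questionnaire will be reminded by email after two weeks", which applies only to a questionnaire that has already been sent.

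Section 5.4 describes cyst-related events broadly; they include changes in follow-up parameters or strategy and decisions for or against treatment.

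Section 10.1.3 says that the email address "will only be used to send an email to the patient after every visit". On subjects who withdraw, section 6.6 says only: "These subjects will receive routine care from their treating physician".

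Section 3 sets inclusion from September 2014 to August 2023, the end of follow-up in August 2024 and the first analysis in September 2017. Section 8 makes that first report purely descriptive on the section 6.1 endpoints. It is also the input to the MISCAN model and to the decision on follow-up frequency after year 5. Section 8.3 plans a multilevel repeated-measures model for the patient-reported outcomes.

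**The concern.** Table V asks whether check-ups are burdensome and whether the next one is dreaded. Such attitudes plausibly influence whether a patient attends, and in years 1 to 3 attendance decides whether the patient is asked. Measurement may then depend on the quantity being measured. The entry questionnaire does not fill the gap, because it precedes the study's follow-up visits and cannot record the experience of them.

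This is a data-collection rule and not a matter of analysis. The model in section 8.3 handles unequal numbers of answers, but it corrects for selective loss only if earlier answers explain that loss. The 2017 report has no model at all. Answers that were never requested cannot be recovered later.

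**Working it through.** **1. What each patient is sent in the first three years** (intervals from section 6.3)

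- Annual visits: entry + months 12, 24, 36 = 4 questionnaires.
- New cyst of at least 1 cm: entry + months 6, 12, 24, 36 = 5.
- Patient who never returns and has no cyst-related event: entry only = 1.

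**2. Whether the year-5 mailing closes the gap** (dates from section 3)

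- The first inclusion is in September 2014, so the earliest year-5 mailing is September 2019, two years after the September 2017 analysis. Post-entry burden data in that report can come only from visits and events.
- A patient included in September 2019 or later reaches year 5 in September 2024 or later, after follow-up ends in August 2024. Inclusion lasts 9 years, and September 2019 to August 2023 is 4 of them. If accrual is uniform (an assumption), 4/9 = 44% of entrants have no year-5 mailing. Those among them who miss all visits and have no event give no post-entry answer.

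**3. Loss rates**

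The protocol states no figure for the burden endpoint. The only loss figures are in section 4.4: 15% of "patients included in the first year, 10% of those included in the second year, and 5% included in the third year", used there to support more than 1000 patient-years from 250 Dutch inclusions per year. With mid-year entry (2.5, 1.5 and 0.5 years) and lost patients credited with half their time:

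250 × [(0.85 × 2.5 + 0.15 × 1.25) + (0.90 × 1.5 + 0.10 × 0.75) + (0.95 × 0.5 + 0.05 × 0.25)] = 250 × 4.225 = 1056.

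This reproduces the protocol's figure. Crediting lost patients with no time gives 250 × 3.95 = 987.5.

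Loss over the three inclusion years is 250 × (0.15 + 0.10 + 0.05) = 75 of 750, or 10%. The 15% is the first-year cohort alone.

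**4. Size and sign of the error at one time point**

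Let d be the share not attending, a the proportion burdened among attenders and b the proportion among non-attenders. Then:

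true = (1 - d)a + d·b, observed = a, error = observed - true = -d(b - a).

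The protocol gives neither a nor b. Assume a = 20% and vary b:

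| d | b = 10% | b = 20% | b = 40% | b = 60% |
|---|---|---|---|---|
| 10% (three-year average) | +1 | 0 | -2 | -4 |
| 15% (first-year cohort) | +1.5 | 0 | -3 | -6 |
| 30% (assumed, to cover skipped visits) | +3 | 0 | -6 | -12 |

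Errors are in percentage points. For example, with d = 15% and b = 60%, true = 0.85 × 20% + 0.15 × 60% = 26% against 20% observed, an error of -6. The sign depends entirely on b - a.

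**5. Sections 6.3 and 10.1.3 side by side**

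Section 6.3 needs the email address for mailings at entry, after visits, after events, at years 5 and 10, and for the reminder. Section 10.1.3 restricts it to a mailing after each visit. Read literally, the two cannot both be followed.

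**The case against.** Visit-anchored mailing is a defensible choice. Several Table V items concern the check-up visit and the imaging, and are best answered soon after them. A series sent only at fixed dates would mix recall periods. This stands, and it is why the post-visit mailings should remain.

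Four stronger readings are tempting, and the protocol does not support them:

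- **Only attended visits trigger a questionnaire.** There are also mailings at entry, after cyst-related events, and at years 5 and 10. Because section 5.4 counts a change in strategy as an event, a recorded decision to stop or reduce surveillance could itself trigger one. The gap concerns mainly patients who drop away without such a record.
- **The burden estimate is biased low.** The protocol says nothing about why patients stop or how burdened they are. Some may stop because they worry little, are ill or have moved, and the error can then be zero or upward.
- **The change would recover the whole error calculated above.** The section 4.4 rates describe loss to follow-up in all Dutch participants, not silent non-attendance among questionnaire recipients. Patients lost or withdrawn from the study would not be reached by any schedule, and those who attended before stopping have already given some answers.
- **Unequal questionnaire counts are a defect.** The 4 against 5 scheduled questionnaires follow from cyst size, which is recorded at baseline, and a multilevel model accommodates such imbalance.

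The protocol also has safeguards: physicians are reminded of follow-up dates (5.4, 6.3), compliance is actively encouraged (9.4), and visit frequencies and losses are reported (8.1). These may reduce non-attendance or show its extent, but they do not supply the missing answers. Section 10.1.3 is probably loose privacy wording. It shows a mismatch to be reconciled and does not confirm a visit-only rule.

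**Conclusion.** The point holds as selective non-measurement. Between entry and year 5, a patient who skips or stops surveillance without a recorded cyst-related event is not asked about burden. The 2017 descriptive report is affected, and so are patients included after August 2019.

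Underestimation of burden is plausible but not shown. With 20% burdened among attenders and 10% to 60% among non-attenders, the error is +1 to -4 points at 10% non-attendance and +1.5 to -6 points at 15%. These figures assume the two burden proportions, borrow the section 4.4 loss rates as the non-attending share, and describe a single time point. Without data from non-attenders, even the sign cannot be learned. The change is worth making because it is cheap and the gap cannot be repaired afterwards.

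**What to change.** In section 6.3, keep the post-visit and event mailings. Add an automatic mailing at 12, 24 and 36 months from entry whenever no visit-triggered questionnaire was sent around that time, with the window stated. Include patients who stop surveillance but keep consent for questionnaires. Add one item on whether and why visits were missed or surveillance stopped. Record the time since the last visit with every questionnaire, and report burden by attendance status, in the 2017 report as well.

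Reconcile section 10.1.3 with the entry, event, reminder, 5-year and 10-year mailings of section 6.3 and with the added one.

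The cost is a change to the mailing rule, one more questionnaire item, matching wording on email use and consent, and a few more emails. Some answers will no longer come directly after a visit, which is why the time since the last visit must be recorded.

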3. STUDY DESIGN

The study is designed as a prospective international multicenter cohort study, which will be coordinated by the department of Gastroenterology and Hepatology of the Erasmus University Medical Center of Rotterdam, the Netherlands. The study will run for ten years. Patients with a pancreatic cyst that requires surveillance will be included from September 2014 until August 2023. Follow-up will continue until August 2024. The first analysis will be conducted in September 2017, after three years, to provide data for the MISCAN model.

Figure 1; Study Flowchart

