5.4 Data collection

Treating physicians will be asked to fill out an online case record form regarding the choice and outcome of the imaging studies, serum and cyst fluid analysis, and the clinical condition of the patient. Patients will fill out questionnaires regarding their quality-of-life and the burden of cyst surveillance.

Any cyst related event will be recorded (i.e. changes in follow-up parameters or strategy, additional imaging studies, reaching an indication for cyst resection, the decision for or against treatment (with motivations), surgical procedures, complications of surgery, pathological outcome). If conservative management is chosen although resection criteria

are met, the argumentation for this decision will be noted. Cyst follow-up will be continued in this group and the subsequent outcome will be monitored. Data collection will continue until August 2024. The database will not only be used for data analysis, but will also automatically generate reminders to the treating physician, regarding follow-up dates.

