8.3 Multivariate analysis

Multivariate survival analysis will only be performed if the number of events will be > 30 . This is expected to be the case for the primary endpoint. The potential risk factors, given above, will have first interest. A statistical program (MPlus) will be used to perform multilevel analysis of longitudinal data (repeated measures), to analyze changes over time for the different patient reported outcomes, such as cancer worries, anxiety, and depression[20].

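### The questionnaire schedule shifts from visit-triggered to largely event-triggered after year 3, so the planned time trends in worry, anxiety and depression are confounded with the trigger, in a direction the protocol does not determine

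*Protocol*

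**What the plan says.** Perceived burden is named in the primary objective (Protocol section 2) and is a secondary endpoint in section 6.1.2: "The perceived burden of surveillance for participants, as assessed by questionnaires regarding attitude towards surveillance and general anxiety and depression".

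Who is asked and when is set in section 6.3. "Patients with a newly diagnosed cyst will be asked to fill out a questionnaire at home (Table V"), provided they give an email address. It goes out at study entry and "after every follow up visit for the first three years, once after 5 and 10 years, and after cyst related events". Visits follow the surveillance schedule of the same section: "Follow-up is recommended at one-year intervals, except for newly diagnosed cysts with a diameter of ≥ 1 cm", who are seen at 6-month intervals in the first year.

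Events are broad. Section 5.4 states: "Any cyst related event will be recorded (i.e. changes in follow-up parameters or strategy, additional imaging studies, reaching an indication for cyst resection", and the list continues with treatment decisions, surgery, complications and pathology.

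The study window is in section 3: patients are "included from September 2014 until August 2023" and "Follow-up will continue until August 2024".

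Section 8.3 plans a multilevel repeated-measures analysis "to analyze changes over time for the different patient reported outcomes, such as cancer worries, anxiety, and depression". It mentions neither the trigger of a response nor any restriction to scheduled ones.

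**The concern.** During the first three years nearly every response is taken because a visit was due. Later, apart from the fixed points, a response exists only because something happened to the cyst. The events listed in section 5.4 can plausibly change how worried a patient feels. If they do, the mix of responses changes with time since entry, and a model with time but no trigger term attributes part of that change to time. A random patient effect does not remove this, because the trigger varies within a patient.

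At stake is the answer on the long-term burden of surveillance, which matters for judging prolonged follow-up. That is also the period in which scheduled measurements run out.

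**Working it through.** The protocol gives no figure for this analysis, so there is none to reproduce. It gives no event rate and no size or sign for the change in score at an event. Both are assumptions below and are shown over a range.

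**Follow-up per patient.** Take entry as uniform over the 9 years of inclusion (an assumption), with closure at year 10. Follow-up then runs from 1 to 10 years. Per enrolled patient:

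- Patient-years in years 0-3: (7/9) × 3 + (2/9) × 2 = 2.78.
- Patient-years after year 3: (7²/2)/9 = 2.72.
- Of these, after year 5: (5²/2)/9 = 1.39; between years 3 and 5: 2.72 - 1.39 = 1.33.
- Share of patient time after year 3: 2.72/(2.78 + 2.72) = 49%.
- Year-5 questionnaires: 5/9 = 0.56. Year-10 questionnaires: essentially none, since only patients enrolled at the very start get there.

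**Scheduled questionnaires in years 0-3**, for a new cyst of at least 1 cm (entry, 6 months, years 1, 2 and 3): 1 + 1 + 1 + 8/9 + 7/9 = 4.67.

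**Event-triggered share** = rate × patient-years / (rate × patient-years + scheduled questionnaires), with one questionnaire per event and all returned:

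| Events per patient-year | Years 0-3 | After year 3 |
|---|---|---|
| 0.05 | 0.139/4.81 = 3% | 0.136/0.692 = 20% |
| 0.1 | 0.278/4.94 = 6% | 0.272/0.828 = 33% |
| 0.2 | 0.556/5.22 = 11% | 0.544/1.100 = 50% |

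For a patient followed the full 10 years (7 years and two fixed questionnaires after year 3), the later share is 7 × rate/(7 × rate + 2): 15%, 26% and 41%. Strictly between years 3 and 5, and in practice after year 5, it is essentially 100% because no scheduled point falls there.

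**Effect on the slope.** I simulated a flat true course with staggered entry: 800 patients, 3 replicates per setting, between-patient SD 3, residual SD 2.5 (both assumed). The score shift applied only to event-triggered responses. A random-intercept model with time alone gave these slopes in points per year (model SE about 0.02):

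| Events per patient-year | Shift +2 | Shift 0 | Shift -2 |
|---|---|---|---|
| 0.05 | +0.05 | +0.02 | -0.05 |
| 0.1 | +0.10 | +0.01 | -0.08 |
| 0.2 | +0.12 | -0.01 | -0.16 |

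Adding an event-trigger term, or using scheduled responses only, brought the slope to within about 0.02 of zero in every one of these settings. The sign of the false slope is the sign of the shift.

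**The case against.** Four arguments count against the point.

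- **The direction is not known.** A reader might infer that anxiety must appear to rise with time by construction. The protocol does not support that. The events include pathology results and additional imaging, which may reassure. The sign is an input to the calculation, not a result. This stands.
- **Scheduled data do not vanish at year 3.** A reader might also infer that nearly all later responses are event-triggered. That is true of the gaps between fixed points but not of the whole later period, because the year-5 questionnaire remains. A 90% share would need 9 × 0.556/2.72 = 1.8 events per patient-year. Contrasts that leave out year 5 would only return the assumed shift, and section 8.3 plans none. This stands.
- **Section 8.3 is brief, and a statistical analysis plan may supply the trigger term.** Events are recorded, and section 10.1.3 couples the clinical and questionnaire data, so responses could be matched to events later. This stands in part. However, the protocol itself fixes the event-dependent sampling and names the analysis, and no later model can create scheduled measurements after year 5.
- **Burden around events is part of the burden of surveillance.** This is fair, and a reason to report those responses rather than discard them. It is not a reason to let them shape the time trend. The split is also not clean: a change found at a visit may make one response both scheduled and event-triggered.

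Section 10.1.3 also describes an email after each visit without the three-year limit. If questionnaires did continue at every visit, the imbalance would be smaller, but section 6.3 is explicit about the schedule.

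**Conclusion.** The point holds as confounding of time with questionnaire trigger. Following sections 6.3 and 8.3 as written, the event-triggered share grows from about 3-11% to about 20-50% across year 3, under uniform entry and 0.05 to 0.2 events per patient-year. The resulting bias in the trend may be upward, downward or absent, depending on how scores move at events.

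The size is modest. At 0.1 events per patient-year and a 2-point shift, about 0.1 points per year amounts to 0.1 × 5 = 0.5 points over five years, against a total SD of √(3² + 2.5²) = 3.9 in the simulation. It affects a secondary endpoint, in newly diagnosed patients who gave an email address. The event rates, the shift and the SDs are assumptions; the change in schedule is in the text. It should be corrected because the remedy is cheap and the affected period is the one that bears on long-term surveillance.

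**What to change.** In section 8.3:

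- Estimate change over time from the scheduled questionnaires only (entry, visits in years 0-3, year 5 and the few at year 10). Alternatively, keep all responses and include a time-varying indicator for event-triggered ones.
- Report event-triggered responses separately, as the course of scores after an event.
- State that scheduled data support trends to about year 5 only.

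In the questionnaire database, record the trigger of each questionnaire, with a rule set in advance for responses that are both visit- and event-triggered. Reconcile the emailing wording in section 10.1.3 with the schedule in section 6.3.

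The cost is a few sentences and one data field. The downside is slightly fewer responses in the trend model if it is restricted to scheduled questionnaires.

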10.4 End of study report

The investigator will notify the accredited METC of the end of the study within a period of 8 weeks. The end of the study is set in August 2024, when the 10-year follow-up period has ended. In case the study is ended prematurely, the investigator will notify the accredited METC, including the reasons for the premature termination. Within one year after the end of the study, the investigator/sponsor will submit a final study report with the results of the study, including any publications/abstracts of the study, to the accredited METC.

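### The 10-year burden questionnaire falls due after data collection closes, so the schedule as written yields no planned burden data beyond year 5.

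*Protocol*

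**What the plan says.** The questionnaire schedule is in Protocol section 6.3, under Patient questionnaires. Patients with a newly diagnosed cyst who give an email address receive the form at study entry and then "after every follow up visit for the first three years, once after 5 and 10 years, and after cyst related events".

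The calendar is fixed elsewhere:

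- Section 3: "Patients with a pancreatic cyst that requires surveillance will be included from September 2014 until August 2023". The same section says "Follow-up will continue until August 2024" and "The study will run for ten years".
- Section 5.4: "Data collection will continue until August 2024".
- Section 10.4: "The end of the study is set in August 2024, when the 10-year follow-up period has ended".

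The form serves a stated purpose. The primary objective in section 2 defines yield partly in terms of "diagnosed malignancies, cyst evolution, and the perceived burden for participants", and section 6.1.2 makes perceived burden a secondary endpoint. Section 8.3 plans a multilevel repeated-measures analysis of cancer worries, anxiety and depression.

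**The concern.** The ten years in sections 3 and 10.4 are the calendar length of the whole study, from first inclusion to closure. They are therefore an upper limit on any one patient's follow-up. A form due ten years after a patient's own entry needs follow-up at least that long, and nobody can have it.

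The strategy under evaluation is lifelong surveillance, so how patients bear it after many years is a natural part of the question. As the schedule stands, the one measurement planned for late surveillance cannot be made. Nothing else is scheduled after year 5, and what arrives later comes only from patients who have had a cyst-related event. This is not a detail that an analysis plan can settle, because no analysis recovers data that were never collected.

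**Working it through.** **Inputs.** Inclusion from September 2014 to August 2023 and follow-up to August 2024 (section 3); data collection to August 2024 (section 5.4); end of study in August 2024 (section 10.4); questionnaire times (section 6.3). The protocol gives months without days, so both the first and the last day of August are tried.

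**1. The plan's own duration.** September 2014 to August 2024 inclusive is 120 months, or 10 years, which reproduces the stated figure. The inclusion window is 108 months, or 9 accrual years.

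**2. The 10-year form.** Due date = entry date + 10 years. The earliest entry is 1 September 2014, so the earliest due date is 1 September 2024.

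- Close on 31 August 2024: missed by 1 day; longest possible follow-up 9.999 years.
- Close on 1 August 2024: missed by 31 days; longest possible follow-up 9.92 years.

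No entry day reaches 10 years under either reading.

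**3. Would early sending rescue it?** The protocol gives no window, so the windows below are assumptions. The entries are the share of possible entry days (1 September 2014 to 31 August 2023) on which the form could be sent before closure.

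| Sent early by | Close 31 Aug 2024 | Close 1 Aug 2024 |
|---|---|---|
| 14 days | 0.4% | 0% |
| 30 days | 0.9% | 0% |
| 90 days | 2.7% | 1.8% |
| 182 days | 5.5% | 4.6% |

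**4. The 5-year form.** Latest usable entry = August 2024 − 5 years = August 2019. September 2014 to August 2019 is 60 of 108 months: 60/108 = 5/9 = 55.6%. Across the August date variants the share runs from 54.6% to 56.1%. It is a share of calendar accrual, and equals a share of patients only if accrual is even.

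**5. What remains late.** Entrants in the first accrual year have 9 to 10 years of possible follow-up. After their 5-year form, 4 to 5 of those years contain no scheduled questionnaire that can be completed.

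**6. Who a close-out form would reach.** Participants more than 3 years from entry at closure entered by August 2021: 84 of 108 months, or 7 of 9 accrual years (77.8% under even accrual), before loss to follow-up and the restriction to newly diagnosed patients with email. Their time since entry would range from 3 to just under 10 years.

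**The case against.** **The clock may not be the patient's own.** Section 8 places the second analysis after 10 years, and section 10.4 calls August 2024 the end of a 10-year follow-up period; both count from study start. On that usage the 5- and 10-year forms could mean study years 5 and 10, and the latter would already be a close-out form. This stands as an ambiguity. But the list opens at study entry and refers to visits in the first three years, which fits per-patient time better. A clock starting at diagnosis, less than 6 months before inclusion for a new cyst (section 5.1), would let some patients included up to about February 2015 qualify: at most about 6 of 108 accrual months. The text does not say this either.

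**The margin is thin.** True for the first entrants, who miss by 1 to 31 days. The table in the working shows that a tolerance would add very few patients.

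**Burden is still measured.** This also stands. Forms are sent at entry, after every visit for three years, at 5 years and after events, and no endpoint or analysis is defined at 10 years. The burden endpoint is not lost; its planned late measurement is.

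**A reader might infer that the 5-year form is also faulty**, because 4 of 9 accrual years cannot reach it. The protocol does not support that. Open accrual with a fixed close gives later entrants shorter follow-up by design, and no 5-year data are promised for everyone. With the target of 5000 in section 4.4 and even accrual, 5000 × 5/9 ≈ 2,780 entrants could reach 5 years, before restriction to newly diagnosed patients with email and before losses. Nothing shows that to be too few.

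**A reader might also infer that late worry scores will be biased upward**, because late forms follow events. The protocol does not establish a direction: cyst-related events in section 5.4 include changes in strategy and additional imaging, not only bad news. Nor does section 8.3 say that event-triggered and scheduled forms will be pooled.

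**Conclusion.** On the protocol's own dates, and with time counted from study entry, no participant can complete the 10-year questionnaire. The result does not depend on which day in August is meant, and an assumed six-month early window changes it only to about 5.5% of entry days (4.6% if closure is 1 August). After year 3 the 5-year form is the only scheduled burden measurement that can occur. It is available to 5 of 9 accrual years, about 56% of entrants under the assumption of even accrual; the accrual pattern among questionnaire recipients is not given.

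The point is confined to this scheduling conflict between section 6.3 and sections 3, 5.4 and 10.4, and to the resulting absence of planned burden data beyond year 5. It does not extend to the adequacy of the 5-year sample, and no claim is made about the direction of any bias in late worry scores. It merits correction because burden is part of the primary objective and a secondary endpoint, and the remedy is cheap.

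**What to change.** In section 6.3, replace the 10-year form with one close-out questionnaire at the last visit before closure in August 2024. Send it to newly diagnosed participants who are still in follow-up and more than 3 years from entry; those within their first three years already receive a form after every visit. Analyse it by time since entry. State that times are counted from study entry, and that the 5-year form applies only to entrants up to August 2019. Flag event-triggered forms in the database so that they can be separated from scheduled ones.

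The cost is an amended sentence or two, a data flag, and one extra online form of 5 to 15 minutes for those eligible. There are two limits to accept: the close-out sample contains only people still active at closure, and time since entry is tied to entry year, so the two effects cannot be separated on this form alone. Clinical management is not affected.
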